9.3 Missing Data

No missing data will be imputed for the primary analysis and secondary analyses.

Missing data for the KOOS will be treated in agreement with the SF-36, substituting missing values with the average value for the dimension. If more than two items were omitted, the response will be considered invalid.

9.4 Statistical Methodology

9.4.1 Data Summary

Descriptive statistics will be computed for all baseline conditions and demographic parameters. If appropriate, the data will be presented by appropriate subgroups (e.g., center). In general, follow-up data will be summarized according to visit. For parameters

represented by continuous variables (e.g., blood loss, KSS), the summaries will consist of the mean, median, standard deviation, minimum, and maximum values. For categorical variables (e.g., revision), the number and percent in each category will be presented. Ninety percent confidence intervals will be presented where tests of non-inferiority will be performed, otherwise the 95% confidence interval will be presented. Descriptive statistics and statistical comparisons for important demographic, efficacy, and safety variables will be provided in tables.

Statistical analyses utilizing SAS® software version 9.1 or higher will be used.

Sample Size Justification

The Stryker sponsored Triathlon CR study has a mean 10-year KSS function 84 points and a standard deviation of 21, A literature review shows the minimal clinically important difference for KSS function is 6 points⁶⁰, with a 5% type I error rate and a power of 80%, the sample size is 76. By factoring in a 20% attrition rate at 10 years postoperatively, the adjusted sample size will be 95 cases.

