Appendix A Component Listing

Appendix B FDA 510K Clearance Letters

Appendix C Product Labeling

Appendix D Model Informed Consent Form

Appendix E Sample Case Report Forms

Appendix F Patient Retention Program

List of Abbreviations

AE Adverse Event
AP Anteroposterior
AVN Avascular Necrosis
BMI Body Mass Index

CAD Computer Assisted Design
CSM Clinical Study Manager
DCF Data Clarification Form
EDC Electronic Data Capture
FEA Finite Element Analysis
GCP Good Clinical Practice

HIPAA Health Insurance Portability and Accountability Act

KSS Knee Society Score

KOOS Knee and Osteoarthritis Outcome Score

M/L Medio/Lateral
ML Mediolateral
OA Osteoarthritis

PCL Posterior Cruciate Ligament PER Product Experience Report

PI Primary Investigator
QOL Quality of Life
ROM Range of Motion
SC Study Coordinator
SF-12 Short-Form 12
TA Traumatic Arthritis

UHMWPE Ultra High Molecular Weight Polyethylene UKA Unicompartmental Knee Arthroplasty

Study Synopsis

Title	The Triathlon [®] PKR Unicondylar Knee System Outcomes Study
Short Title	Triathlon [®] PKR Study
Protocol Number	66
Phase	Post-marketing
Methodology	This study is a prospective, post-market, multi-center evaluation of the Triathlon [®] PKR unicondylar knee system with an additional retrospective enrolled and prospectively followed cohort of cases.
Study Duration	10-year follow-up for each case
Study Center(s)	A minimum of four centers will participate.
Objectives	Primary: The 10-year mean KSS Function Score is comparable to the Triathlon CR KSS Function Score at 10-years. Secondary: A 10-year Kaplan Meier survival analysis will be presented including only prospective cases.
Additional Data Collection	To compare OR time, hospital stay, blood loss, return to ROM, KSS, activity level, adverse event rates, and radiographic data to UKA.
Reference Therapy	Triathlon CR Stryker Sponsored Study; Clinical Trials NCT 00966979; Survivorship data from national registries will supplement the study survivorship data.
Number of Subjects	A total of 175 cases (knees) will be enrolled. There are 80 cases enrolled from the prospective cohort and a planned minimum 95 cases is the goal from the retrospective cohort.

Inclusion Criteria

- 1) The subject is a male or non-pregnant female 21-75 years of age at the time of enrollment.
- 2) The subject requires a primary cemented unicompartmental knee replacement.
- 3) The subject has a diagnosis of osteoarthritis (OA) or post-traumatic arthritis (TA).

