2.1 Efficacy

2.1.1 Primary

The 10-year mean KSS Function Score is comparable to 84 points (the mean of the Triathlon CR KSS Function Score at 10-years postoperatively). The mean PKR 10-year score is calculated from both the prospective and retrospective cases.

CONFIDENTIAL

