3.1 Study Design

A prospective, post-market, multi-center design will be employed in the first phase. Prospective enrollment closed early due to lack of enrollment and a retrospective arm is initiated to enroll additional cases. Prospective data will be obtained on the retrospective cases to 10-years.

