3.2 Number of Centers

There have been 80 cases enrolled to date in the prospective arm of the study at seven study centers. The number of centers will be determined by the number of cases that are screened successfully into the retrospective cohort of this amendment.

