3.3 Number of Subjects

Prospective enrollment will close with this protocol amendment at 80 cases. The last case was enrolled on January 29, 2018. Retrospective enrollment will be initiated at current study centers who have subjects that meet the enrollment criteria. The number of subjects obtained retrospectively will be a minimum of 95 cases from those implanted by the surgeon prior to the initiation of this study and any cases done after the original enrollment goal was met. If there are insufficient cases at the existing sites, other sites will be considered. These cases will have the Triathlon® PKR Unicompartmental Knee System. A total of 175 cases (knees) will be enrolled, 80 cases from the prospective cohort and a planned minimum of 95 cases from the retrospective cohort.

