9.1 Efficacy

9.1.1 Primary Efficacy Parameters

The primary efficacy parameter is the mean 10-year KSS Function Score combining the prospective and retrospective cases.

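### Does setting 95 as the retrospective minimum, on top of 80 prospective cases, leave the pooled primary test without a sample size that fits it?

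*Combined protocol and SAP*

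**What the plan says.** The Sample Size Justification in section 9.4.1 takes a 10-year mean KSS function of 84 and an SD of 21 from the sponsor's Triathlon CR study. With a margin of 6, a 5% type I error and 80% power it arrives at 76, and then: "By factoring in a 20% attrition rate at 10 years postoperatively, the adjusted sample size will be 95 cases".

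The primary endpoint covers both cohorts. Section 2.1.1 says "The mean PKR 10-year score is calculated from both the prospective and retrospective cases", and section 9.1.1 says "The primary efficacy parameter is the mean 10-year KSS Function Score combining the prospective and retrospective cases". Section 9.1.4 gives one decision rule on that mean: the lower limit of a two-sided 90% confidence interval must exceed 78.

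For enrolment, section 3.3 says "A total of 175 cases (knees) will be enrolled, 80 cases from the prospective cohort and a planned minimum of 95 cases"; the second group is the retrospective one. The Study Synopsis agrees: "There are 80 cases enrolled from the prospective cohort and a planned minimum 95 cases is the goal from the retrospective cohort". On sites, section 3.2 says "The number of centers will be determined by the number of cases that are screened successfully into the retrospective cohort of this amendment", and section 3.3 adds "If there are insufficient cases at the existing sites, other sites will be considered".

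**The concern.** The same figure seems to do two jobs. In section 9.4.1, 95 is the enrolment that gives the primary test 80% power. In section 3.3 it is the floor for one of the two cohorts entering that test. If 95 is the pooled requirement, the 80 prospective cases leave only 15 to find, not 95. If it is meant for the retrospective cohort alone, no analysis of that cohort alone is planned. Nowhere is a reason given for 175, or its power.

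The retrospective count also bears on how many centers take part. If the floor of 95 has no link to the primary test, sites might be added to reach a number the test does not need, or a smaller cohort might be judged inadequate when it is not. A single attrition rate is also used for both cohorts, although retrospective cases enter at five years or later (section 7.1), with deceased and revised patients already screened out (section 10.1).

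**Working it through.** **Inputs.** SD 21, margin 6, type I error 5%, power 80% and attrition 20% (section 9.4.1); lower limit of a two-sided 90% interval, so one-sided 5% (section 9.1.4); 80 prospective and at least 95 retrospective cases (section 3.3). The true mean is taken as 84, which the calculation implies but does not state.

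**The plan's own figure.** For a one-sample non-inferiority test of a mean, normal approximation:

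n = (21 × (1.645 + 0.842) / 6)² = 75.7, rounded up to 76. Then 76 / 0.8 = 95.

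Both figures reproduce. An exact t calculation gives 78 evaluable and 98 enrolled, a trivial difference.

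**Power for other evaluable numbers.** Power = Φ(6√n / 21 − 1.645).

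| Cases counted | Evaluable n | Power |
|---|---|---|
| 80 prospective only, 20% attrition | 64 | 73.9% |
| 95 retrospective only, 20% attrition | 76 | 80.1% |
| 175 pooled, 20% attrition | 140 | 95.9% |
| 175 pooled, 40% attrition | 105 | 90.0% |

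**Two readings of the 95.**
- As the pooled total: the 80 prospective cases give 64 evaluable, 12 more are needed, and 12 / 0.8 = 15 retrospective cases would do. The plan asks for at least 95.
- As the retrospective cohort's own size: that cohort reaches 80.1% by itself, and the 64 evaluable prospective cases raise the pooled test to 95.9%.

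On either reading, the plan as written exceeds its stated 80%.

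**Attrition that differs by cohort.** The documents give no cohort-specific rates, so these are assumed ranges: 20–40% prospective and 5–20% retrospective. The low end is 80 × 0.6 + 95 × 0.8 = 48 + 76 = 124 evaluable (93.8%). The high end is 80 × 0.8 + 95 × 0.95 = 64 + 90.25, about 154 evaluable (97.1%). Overall attrition would have to reach 1 − 76/175 = 56.6% before the evaluable number fell to 76.

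**Sensitivity to the true mean.** Replace 6 by the true mean minus 78:

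| Evaluable n | True mean 84 | True mean 83 | True mean 82 |
|---|---|---|---|
| 76 | 80% | 67% | 50% |
| 112 (80 + 60 cases, 20% attrition) | 92% | 81% | 64% |
| 140 (80 + 95 cases, 20% attrition) | 96% | 88% | 73% |

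The larger number is useful protection if the device does slightly worse than the reference.

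**The case for a change.** The strongest case for a change is operational. Section 3.1 records that "Prospective enrollment closed early due to lack of enrollment and a retrospective arm is initiated to enroll additional cases". If the retrospective cohort also fell short, at 60 cases say, the plan would count it as below its minimum. Yet the pooled test would have 91.6% power at 20% attrition (112 evaluable) and 83.5% at 40% (84 evaluable). A couple of sentences in sections 9.4.1 and 3.3 would show this at almost no cost.

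Part of this stands: no passage says why 95 was chosen for the new cohort or what power 175 gives. The rest is weaker.
- The inputs in section 9.4.1 are those of the primary test, and section 9.1.1 defines that test on both cohorts, so what the 95 serves can be read from the plan.
- The trigger for other sites has a basis. It follows the minimum of 95 within section 3.3, and it only commits the sponsor to consider them.
- Slow prospective recruitment says little about finding already implanted knees by chart review, and the documents give no count of available cases.
- Writing a smaller retrospective requirement beside an unchanged minimum of 95 would create two competing targets. The smaller one would hold only if the true mean is 84. It would also ignore losses from the per-protocol exclusions in sections 9.4.3 and 9.4.5, which the 20% attrition is not said to cover.

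**Conclusion.** The concern does not call for a change. No stated figure is wrong and no passages contradict each other: one section gives the number needed and another plans to enrol more. Followed as written, the plan gives the pooled test about 96% power against a stated 80%, assuming SD 21, a true mean of 84, 20% attrition in both cohorts and independent knees. Power stays at 90% with 40% attrition in both. It is lower if the true mean is below 84 or if per-protocol exclusions are many, which favours keeping the surplus.

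What remains is an unexplained surplus. A statistician reading sections 9.1 and 9.4.1 together would take the 95 as the need of the pooled test and the 175 as exceeding it. Spelling that out would alter neither enrolment, endpoint, decision rule nor conclusion.

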9.4.2 Interim Analyses and early Stopping Considerations

No interim analysis is planned.

9.4.3 Efficacy Patient Populations

Per Protocol Population:

All subjects other than those censored who received the Triathlon® PKR Unicondylar Knee System. Data for patients where a protocol deviation occurred which could affect patient outcome will not be included.

The primary and secondary efficacy analyses will be based on the per protocol population.

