9.4.4 Safety Patient Population

Safety Population

The safety population will include all non-censored subjects who received the Triathlon® PKR Unicondylar Knee System.

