9.4.5 Censored Cases

Data for patients where a protocol deviation occurred which could affect patient outcome will be censored from the Efficacy and Safety Patient Populations. They will be reported on separately.

If a case receives a unicompartmental knee arthroplasty in the contralateral compartment of the study knee, this case will be considered a deviation and censored from analysis for all areas except survivorship. This case will be included in the survivorship analysis only.

10 Study Procedures

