11.5 Protocol Deviations

Any deviation from this protocol categorized as a 'Major Protocol Deviation' will be recorded by the Sponsor and must be reported to the investigational center's overseeing IRB according to their reporting procedures. Major protocol deviations for this study may include the following; this list may not be all-inclusive:

- Informed consent deviations, including but not limited to:
 - Study procedures performed prior to informed consent
 - Incorrect informed consent version used
- Patient enrolled does not meet the inclusion/exclusion criteria
- Protocol specified study component(s) not implanted
- Off label component usage

If the center anticipates a possible protocol deviation, the investigator or SC should contact Stryker for guidance.

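### The 10-year KSS conclusion rests only on a per-protocol set that drops outcome-affecting deviations and contralateral-compartment UKAs, with no all-implanted result beside it

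*Combined protocol and SAP*

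**What the plan says.** Section 9.4.3 defines one efficacy population and gives it both roles: "The primary and secondary efficacy analyses will be based on the per protocol population". Its exclusion rule is: "Data for patients where a protocol deviation occurred which could affect patient outcome will not be included".

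Section 9.4.5 applies the same rule more widely. Such cases "will be censored from the Efficacy and Safety Patient Populations", and "They will be reported on separately". It then adds a specific trigger, a UKA placed in the other compartment. For a knee with that event the rule is: "this case will be considered a deviation and censored from analysis for all areas except survivorship". The next sentence confirms that the case stays in the survivorship analysis.

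Section 9.4.4 does not supply a wider set: "The safety population will include all non-censored subjects". Section 11.5 gives examples of major deviations, but introduces them with "Major protocol deviations for this study may include the following; this list may not be all-inclusive", and 9.4.3 does not refer to that list.

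The primary test (9.1.4) asks whether the lower limit of a two-sided 90% confidence interval for the mean 10-year KSS Function score exceeds 78. The secondary parameter (9.1.2, 9.1.5) is revision or removal of any component, shown by Kaplan-Meier. The synopsis compares the lower limit of a 90% interval for 10-year success with 80% and 88%. Section 9.3 imputes nothing for either analysis.

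**The concern.** The primary test compares one mean with a constant. There is no control arm in which similar exclusions could offset each other, so removing knees that score below the rest raises the estimate directly.

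Three features make this possible here:

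- **The rule turns on judgement.** The plan names no complete list of excluding deviations, no person who decides, no time for the decision and no masking to scores. Every subject has the study device and follow-up is open, so a decision could be made with outcomes in view. Deviation status is not always clear either. The alignment limit is 15 degrees in the synopsis and 4.1 but 10 degrees on the inclusion form in Appendix E, so a knee at 12 degrees meets one and fails the other. Those passages need to be reconciled.
- **One trigger is probably an event after treatment.** Exclusion criterion 3 in 4.2 already bars a knee with a prior contralateral-compartment reconstruction. The natural reading of 9.4.5 is therefore a later UKA. Its KSS is dropped even if a 10-year score was recorded.
- **Nothing wider is planned.** Per-protocol analysis is usual in non-inferiority work as one of two analyses. Here it is the only one, and the safety set has the same exclusions.

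At stake is whether a reader can tell how far a non-inferiority claim depends on who was left out.

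**Working it through.** **1. The plan's own figure.** Inputs from Sample Size Justification (under 9.4.1): SD 21, margin 6, type I error 5%, power 80%. The 90% two-sided interval in 9.1.4 makes the test one-sided at 5%. The one-sample formula gives

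n = [21 × (1.6449 + 0.8416) / 6]² = 8.703² = 75.7, rounded up to 76, and 76 / 0.80 = 95.

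Both stated figures reproduce. The point below does not change them.

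**2. Which knees enter which analysis (9.4.3 to 9.4.5).**

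| Analysis | Outcome-affecting deviation | Contralateral-compartment UKA |
|---|---|---|
| 10-year KSS Function mean (primary) | removed | removed |
| Kaplan-Meier survivorship (secondary) | removed | kept |
| Safety | removed | removed |

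No row keeps both. The two survival curves in 9.1.5 differ by cohort (prospective only, or both cohorts), not by analysis set, so neither is an all-implanted curve as the plan stands.

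**3. Effect on the primary test.** Let f be the share of evaluable knees excluded and d the number of points by which they score below the retained knees. Then

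all-implanted mean = (1 − f) × PP + f × (PP − d) = PP − f·d,

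so the per-protocol mean (PP) is higher by f·d. If the all-implanted mean is exactly 78, the chance of declaring non-inferiority is

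Φ( f·d / SE − 1.645 ), with SE = 21 / √[n(1 − f)].

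Assumptions: SD 21 in the retained knees; n = 140, which applies the plan's 20% attrition to all 175 cases (175 × 0.80); f and d chosen for illustration, because the documents give neither.

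- f = 2%, d = 10: shift 0.2; SE = 21/√137.2 = 1.793; Φ(0.112 − 1.645) = 6.3%.
- f = 5%, d = 20: shift 1.0; SE = 21/√133 = 1.821; Φ(0.549 − 1.645) = 13.7%.
- f = 10%, d = 20: shift 2.0; SE = 21/√126 = 1.871; Φ(1.069 − 1.645) = 28.2%.

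With n = 76, the same three settings give 5.9%, 10.7% and 19.6%.

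These values are not limits. A wider gap goes further (f = 10%, d = 30, n = 140 gives 48.4%). If excluded knees score the same as the rest (d = 0), the mean does not shift; if they score higher, the bias reverses.

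**The case against.** Much can be said for the plan, and part of it stands.

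- **Survivorship.** A reader might infer that the contralateral-UKA rule raises the survival rate, or that 9.4.3 and 9.4.5 contradict each other. The documents support neither. Section 9.4.5 keeps these knees in survivorship explicitly; it is a stated exception to a general rule. What remains is that knees with other outcome-affecting deviations leave the survival analysis.
- **Disclosure.** A reader might infer that excluded cases vanish. They do not, since 9.4.5 promises separate reporting. That puts them in view, but it is not a combined estimate and does not show whether the conclusion survives their return.
- **Nature of the deviations.** The examples in 11.5 (consent errors, ineligibility, wrong components, off-label use) are mostly fixed at enrolment or surgery, and a wrong consent version has no evident link to KSS. This lowers the likely bias, but the list is open-ended and 9.4.3 does not adopt it.
- **Table I.** It is tempting to use its arthritis-progression rates to predict how many knees the contralateral rule removes. They do not count later contralateral-compartment UKAs, the entries mix in revisions, and the 30% value comes from a hemiarthroplasty series in patients under sixty. No number can be drawn from it.
- **Target of estimation.** With a second implant in the knee, function is no longer due to the study device alone, so excluding these knees is defensible as one analysis. It does not justify having no other.
- **Limited recovery.** Knees terminated for revision (10.3), or for a non-intact ACL (surgical details form), will have no 10-year KSS to add. The all-implanted KSS analysis can only use observed scores.

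**Conclusion.** The point holds for the primary endpoint and, in narrower form, for survivorship. The 10-year KSS Function conclusion rests on one set, defined by a judgement-based exclusion and, on the natural reading, by a post-index event. No planned analysis shows what happens without those exclusions.

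The size is unknown. Under the assumptions above (all-implanted mean 78, SD 21, 140 evaluable knees), the false-claim rate moves from a nominal 5% to about 6% with few, mildly worse exclusions and to about 28% with 10% excluded scoring 20 points lower. This shows that the design is sensitive to the exclusions; it does not predict what will happen. A reader might infer that the result will be materially biased. The documents do not support that, because they give no exclusion share, no scores for excluded knees, and no certainty about the direction.

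This is a cheap improvement.

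**What to change.** In 9.4.3, define an all-implanted set: every enrolled knee that received the device. Then:

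- Report the mean 10-year KSS Function score and its 90% confidence interval against 78 in every such knee with an observed 10-year score, including contralateral-UKA knees, next to the per-protocol result.
- State in the conclusion whether the two results agree. Making non-inferiority conditional on both is a stricter rule that could be debated; it is not needed here.
- Base Kaplan-Meier survivorship on the all-implanted set. The exception in 9.4.5 is then no longer needed for that analysis.

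As an optional addition, list the excluding deviations in advance and have them judged without sight of the scores.

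Cost: SAP wording and one repeat run on data already being collected. No new subjects are needed, and the 76 and 95 are unchanged. The downside is that the estimate may be slightly less favourable.

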9.4.4 Safety Patient Population

Safety Population

The safety population will include all non-censored subjects who received the Triathlon® PKR Unicondylar Knee System.

